**Asymptomatic**

Participants with a ATTR variants that are asymptomatic and either have a CCI score  $<$ I or missing.

**Unclassified Phenotype**

Participants who do not qualify as predominately cardiac, neurologic, mixed phenotype or are asymptomatic.

Additional details about the phenotypes can be found in Table 3 below.

**Table 3: Phenotype classification**

Phenotype	Genotype	Symptomatic	Cardiac symptoms with medical history="cardiovascular"	Cardiac symptoms ongoing status	Cardiac symptom severity	Neurologic symptoms with medical history="Neurologic" or "GI"	Neurologic symptoms ongoing status	Neurologic symptoms severity	mPNDscore
Predominantly cardiac	ATTRwt	Yes/ No	Rhythm disturbance/Heart failure/Dyspnoea	Either ongoing or not ongoing	Any severity	Erectile dysfunction/constipation/carpal tunnel syndrome	Ongoing/or not	Any severity related or not	< 1 or missing
	ATTRwt	Yes/ No	Rhythm disturbance/Heart failure/Dyspnoea	Either ongoing or not ongoing	Any severity	Any neuro/GI symptoms other than Erectile dysfunction/constipation/carpal tunnel syndrome	Ongoing /or not	Any severity if unrelated, or Mild related, possibly related	< 1 or missing
	ATTRv	Yes	Rhythm disturbance/Heart failure/Dyspnoea	Either ongoing or not ongoing	Any severity	No neuro or GI TTR related or possibly symptoms	none	none	< 1 or missing
Predominantly neurologic	ATTRv	Yes	Any cardiac symptoms except Rhythm disturbance/Heart failure/Dyspnoea or No cardiac symptoms	Either ongoing or not ongoing	Any severity	Any neuro/GI symptoms including Erectile dysfunction/constipation/carpal tunnel syndrome	Ongoing	Any	1 or Missing
	ATTRv	Yes	Any cardiac symptoms except Rhythm disturbance/Heart failure/Dyspnoea or No cardiac symptoms	Either ongoing or not ongoing	Any severity	Missing	Missing	Missing	1

Mixed	ATTRwt	Yes	Rhythm disturbance/Heart failure/Dyspnoea	Either ongoing or not ongoing	Any severity	Any neuro/GI symptoms excluding Erectile dysfunction/constipation/carpal tunnel syndrome	Ongoing	Moderate/Severe related or possibility related	1 or missing with symptoms as described
	ATTRv	Yes	Rhythm disturbance/Heart failure/Dyspnoea	Either ongoing or not ongoing	Any severity	Any neuro/GI symptoms including Erectile dysfunction/constipation/carpal tunnel syndrome	Ongoing	Any	1 or missing (if missing must have symptoms as described)

**The other subgroups to be considered are as follows:**

- CCI [REDACTED]
- Severe hepatic impairment (only to be used corresponding to tafamidis treated set). The patients with severe hepatic impairment at baseline will be identified by any of the following:
  - The following pre-coded terms on the Gastrointestinal medical history and the Gastrointestinal general assessment forms: Hepatitis, Cirrhosis, Gastrointestinal malignancy, Hepatotoxicity, Other hepatic impairment having severity scale as “severe”.
  - The following terms appearing in the database as entered on the Other Gastrointestinal Medical History or General Assessment forms at baseline and assessed as ‘severe’: “severe impaired hepatic function”, “severe hepatic dysfunction”, “severe liver dysfunction/liver failure”. Other similar terms as identified during the final database lock of this study may be investigated to identify patients with severe hepatic impairment at baseline.
- Patients not on tafamidis at the time of enrollment on THAOS who had a liver transplant prior to enrollment on THAOS
- Patients not on tafamidis at the time of enrollment on THAOS who had a liver transplant after enrollment on THAOS
- Patients not on tafamidis at the time of enrollment on THAOS without any liver transplant either before or after enrollment on THAOS
- Patients treated with tafamidis at any time in THAOS and with a liver transplant prior to first dose of tafamidis
- Patients treated with tafamidis at any time in THAOS and with a liver transplant after the first dose of tafamidis
- Patients treated with tafamidis at any time in THAOS and never had a liver transplant
- Off-label use of 80/61 milligram (mg) of tafamidis (only to be used corresponding to tafamidis treated set) defined as:
  - Patients not classified as predominantly cardiac or mixed phenotype at the first date of dosing with a dose of 80/61 milligram (mg) of tafamidis.
- Predominantly neurologic at baseline who become mixed phenotype post baseline\*
- Predominantly cardiac at baseline who become mixed phenotype post baseline\*

Sample size in a subgroup needs to be at least 10 in order to have sufficient data to provide descriptive statistics, listings will be provided for smaller subgroups.

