### 9.3.1. Study Assessments

- Written informed consent/assent.
- Inclusion/exclusion criteria.
- Patient demographics (year of birth, gender, ethnic origin, race (if allowed by local regulations)).
- TTR genetic test results.
- Family disease history (previous family history of ATTR amyloidosis).

- Medical history (past and current signs, symptoms, and medical diagnoses).
- Annual medical assessment (current signs and symptoms).
- General examination (weight/height, vital signs, CCI [REDACTED]).
- Concomitant medications (category, indication, start and stop dates).
- Hospitalizations (admission and discharge dates, reason for hospitalization).
- Transplant history and complications (date(s) of transplant(s), organ(s) transplanted, information on complications).
- AE/SAE reporting for tafamidis-treated subjects.
- Events of interest (as listed in Table 1, Summary of Safety Concerns to be Assessed in THAOS).
- Clinical laboratory data (hematology, clinical chemistry, liver function tests, thyroid function tests).
- Urinalysis (includes glomerular filtration rate [GFR]).
- Cardiovascular assessments (electrocardiogram, echocardiogram, Holter monitoring, CCI [REDACTED]).
- Neurologic assessments (deep tendon reflexes, sensation [pinprick, soft touch, vibration, and position sense], motor strength, nerve conduction studies).
- Eye examination (intraocular pressure, vitreous, presence of opacities).
- Body composition (total bone mineral density and content, total lean and fat mass).
- CCI [REDACTED]
- Patient death (data on patient death will be collected independently of the visit schedule).

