**Table 1 Summary of ongoing tafamidis safety concerns to be addressed in THAOS**

Level of Risk or Missing Information	Specific Concerns
Important potential risks	Hepatotoxicity Reproductive and developmental toxicity and lactation Changes in thyroid function, particularly in pregnant women
Important missing information	Safety and efficacy in patients with ATTR-PN variants other than Val30Met (B3461029 substudy) CCI █ Patients with severe hepatic impairment

Note: The important identified risks (Urinary tract infections, Diarrhea, Upper abdominal pain and Vaginal infections); important potential risks (Hypersensitivity reactions); and missing information (Safety and efficacy in elderly patients and Longer-term safety) have been removed from the list of ongoing safety concerns from the tafamidis EU Risk Management Plan (RMP) Update (v 9.3), approved on 17 February 2020 and therefore will not be addressed in the final clinical study report (CSR) for THAOS.

All AE/SAE data will be collected for patients treated with commercially available tafamidis; patients receiving tafamidis as part of their participation in an open-label clinical study will have AE/SAE data collection through the open-label clinical study; reporting of Health Events of Interest will be available for patients not treated with tafamidis.

All visits are intended to be outpatient visits. Table 2 presents the data collected throughout a patient's participation in THAOS per the case report form (CRF). All assessments listed in Table 2 are recommended, but not required and will be determined by the investigator.

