**Table 2 Data Collection per Visit**

Case Report Form	Eligibility/ Baseline Visit	Return Visits	Retrospective Visits (optional)	Final Visit c
Written informed consent/assent	X	--	--	--
Inclusion/exclusion criteria	X	--	--	--

PFIZER CONFIDENTIAL

Case Report Form	Eligibility/ Baseline Visit	Return Visits	Retrospective Visits (optional)	Final Visit c
Patient demographics date of birth, gender, ethnic origin	X	--	--	--
Clinical trial and compassionate use program participation (log format)	X	X	X	
TTR data genetic test results, tissue biopsy	X	--	--	--
Family history of ATTR amyloidosis	X	--	--	--
Medical history past and current signs, symptoms and medical diagnoses	X	--	--	--
Annual updated medical assessment current signs and symptoms	--	X	--	X
General exam weight/height, vital signs, CCI [REDACTED]	X	X	X	X
Concomitant medications (log format) category, indication, start and stop dates	X	X	X	X
Tafamidis treatments (log format) dose, start and stop dates	X	X	X	
Hospitalizations (log format) admission and discharge dates, reason for hospitalization	--	X	X	X
Transplant history and complications (log format) date(s) of transplant(s), organ(s) transplanted, information on complications	X	X	X	X
Adverse events	X	X	X	X
Laboratory data Hematology, clinical chemistry, urinalysis, including glomerular filtration rate [GFR]	X	X	X	X
CCI [REDACTED]	■	■	■	■
[REDACTED]	■	■	■	■
Nerve conduction studies: Upper Extremity, Lower Extremity				
Renal/bladder ultrasound a residual volume, number and size of kidneys, echogenicity	X	X	X	X

Case Report Form	Eligibility/ Baseline Visit	Return Visits	Retrospective Visits (optional)	Final Visit c
Eye examination a intraocular pressure, vitreous, presence of opacities	X	X	X	X
Body composition a total bone mineral density and content, total lean and fat mass	X	X	X	X
CCI [REDACTED]	■	■		X
Patient death b			X	
Patient discontinuation b			X	
Patient status update b			X	

a Printed assessment worksheets will be available to provide to outside specialists performing assessment(s).

b Data on patient deaths, discontinuations, and status assessments will be collected independent of the visit schedule.

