### Adverse Events & Serious Adverse Events

All adverse events will be coded according to the latest Medical Dictionary for Regulatory Activities (MedDRA) version at the time of analysis.

Adverse events (all causality and treatment-related) will be summarized by severity and starting dose using the tafamidis treated set by phenotype at enrollment and overall, CCI [REDACTED] and either predominantly cardiac or mixed phenotype at enrollment, tafamidis treated set for patients who had severe hepatic impairment at baseline, tafamidis treated set by liver transplantation status (liver transplant prior to first dose of tafamidis/liver transplant after the first dose of tafamidis/no liver transplant).

Separate summaries will be provided for all AEs, treatment related AEs, all SAEs, treatment related SAEs, AEs leading to dose reduction, AEs leading to withdrawal of tafamidis (temporarily or permanently, or delayed) and AEs leading to tafamidis dose interruptions.

Listings will be provided for adverse events corresponding to all enrolled patients and for patients with off-label usage of tafamidis. A separate listing of SAEs will also be provided for tafamidis treated set.

The following AE summary tables will be provided corresponding to some of the important potential risks using the tafamidis treated set.

- For **hepatotoxicity** using the search criteria: MedDRA SMQ (Standardized MedDRA Query) [Broad and narrow] Drug related hepatic disorders – comprehensive search. The derivations and conventions related to the search criteria will follow the programming specifications done in the Periodic Safety Update Report (PSUR) 12 for tafamidis.
- For **reproductive and developmental toxicity and lactation**:
  - MedDRA SMQ (Broad and narrow): Congenital, familial and genetic disorders; Foetal disorders; Neonatal disorders, Neonatal exposures via breast milk.
  - MedDRA Preferred terms (PTs): Exposure during pregnancy, Exposure via father, Foetal exposure during delivery, Foetal exposure during pregnancy, Foetal exposure timing unspecified, Maternal exposure before pregnancy, Maternal exposure during delivery, Maternal exposure during pregnancy, Maternal exposure timing unspecified, Drug exposure before

- pregnancy, Exposure via breastmilk, Maternal drug affecting foetus, Maternal exposure during breastfeeding
- The derivations and conventions related to the search criteria will follow the programming specifications done in the PSUR 12 for tafamidis.

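### The severe hepatic impairment subgroup can include patients with no current hepatic impairment: gastrointestinal malignancy qualifies alone, and no ongoing condition is required

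*SAP*

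**What the plan says.** SAP section 5.4, under the other subgroups, restricts this subgroup to the tafamidis treated set and opens with "The patients with severe hepatic impairment at baseline will be identified by any of the following". Two routes follow.

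- **Pre-coded terms.** The search covers "The following pre-coded terms on the Gastrointestinal medical history and the Gastrointestinal general assessment forms", and the terms are "Hepatitis, Cirrhosis, Gastrointestinal malignancy, Hepatotoxicity, Other hepatic impairment having severity scale as" severe.
- **Free text.** The search covers other gastrointestinal entries on the medical history or "General Assessment forms at baseline and assessed as" severe. The example terms here are all hepatic.

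Neither route asks for liver involvement by a tumour, a liver function result, or an ongoing condition. SAP Table 2 describes the medical history form as holding "past and current signs, symptoms and medical diagnoses" and has it completed only at the eligibility/baseline visit. Protocol section 9.3.1 describes its content in the same way.

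SAP Table 1 lists "Patients with severe hepatic impairment" as important missing information. Protocol Table 1 lists the same item, and neither table's footnote removes it. SAP section 8.2.6 then reports survival, exposure, adverse events and deaths for the "tafamidis treated set for patients who had severe hepatic impairment at baseline".

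**The concern.** The subgroup is meant to show what happens when patients with severely impaired liver function take tafamidis. The definition instead selects on a diagnosis and its recorded grade. One of the five pre-coded terms is not a liver condition: a severe bowel cancer meets the rule as written. The history form adds a second gap, because nothing in the rule separates a severe hepatitis that resolved before treatment from one still present when treatment starts.

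This is a regulatory missing-information population, and the final report will describe it through this one subgroup. Patients with malignancy could raise mortality and adverse event frequencies for reasons unrelated to liver function. Recovered patients could lower them. A reader of the output could not tell which had happened, because the plan does not ask for a breakdown by qualifying term.

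**Working it through.** The plan states no count, sample size or expected event rate for this subgroup, so there is no figure to reproduce. The check is first textual, then illustrative.

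**1. Does malignancy qualify alone?** The lead-in makes any one criterion sufficient. Gastrointestinal malignancy stands in the list as a separate term with no qualifier. On a plain reading, yes.

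**2. Is current status enforced?** The words for baseline status appear in the lead-in and in the free-text route. They show intent, but no rule turns them into an ongoing/resolved filter. The SAP writes such a filter elsewhere:
- The predominantly neurologic phenotype (section 5.4) requires ongoing symptoms.
- Table 3 has ongoing-status columns.
- Section 8.2.4 summarises ongoing and past symptoms separately.

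Timing adds to the gap. Section 8.2 sets the treated-set baseline as the latest value in a window of three weeks either side of starting tafamidis. The history form is completed at enrollment, which may be long before treatment starts.

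**3. What does severe govern?** It may apply to all five pre-coded terms or only to the last. On the second reading, hepatitis, cirrhosis or gastrointestinal malignancy of any grade would qualify.

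**4. How far could outputs move?** Let f be the share of the subgroup without hepatic impairment, and p1 and p0 the event risks in impaired and non-impaired patients. All three are assumed values.

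Reported risk = (1 − f) × p1 + f × p0

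| f | p1 = 40%, p0 = 20% | p1 = 20%, p0 = 40% |
|---|---|---|
| 10% | 0.9×40 + 0.1×20 = 38% | 0.9×20 + 0.1×40 = 22% |
| 25% | 0.75×40 + 0.25×20 = 35% | 0.75×20 + 0.25×40 = 25% |
| 50% | 0.5×40 + 0.5×20 = 30% | 0.5×20 + 0.5×40 = 30% |

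The bias can go either way.

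**5. Reporting thresholds.** Sections 5.4 and 8.1 require at least 10 patients for descriptive statistics. Section 8.1 requires at least 5 events for Kaplan-Meier estimates. If exactly 10 qualify, the expected number truly impaired is 10 × (1 − f), which is 9, 7.5 or 5 for the three shares. One misclassified patient in ten is enough to turn a listing into a summary table.

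**6. Information content.** For an adverse event with an assumed 10% risk, the chance of at least one case among m truly impaired patients is 1 − 0.9^m: 65% for m = 10, 61% for 9, 57% for 8 and 41% for 5. A table headed by 10 patients would suggest the first figure when a lower one may apply.

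**The case against.** Several stronger conclusions are tempting, and the documents do not support them.

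- **That the subgroup consists largely of patients without hepatic impairment.** No count is given for the subgroup or for any term. Only the possibility of inclusion can be shown.
- **That recovered patients are certainly admitted.** The lead-in says baseline, so current status was probably intended. How status and severity are recorded depends on the case report form and its completion guidelines, which are not in these documents. What can be said is that no ongoing rule is written and that a form holding past conditions is searched.
- **That cancer deaths would be read as a tafamidis effect.** Section 8.2.6 reports deaths for this subgroup by primary cause and by relation to ATTR, and lists deaths in the treated set. A cancer death should be visible there. Adverse events are also shown both regardless of cause and as treatment-related. The Kaplan-Meier curve, which is not split by cause, and the all-causality adverse event tables are more exposed.
- **That THAOS has no other route to this safety question.** This SAP supports the final report only. Section 2 refers to separate plans for annual regulatory reporting.

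It is also fair that all analyses are descriptive, with no hypothesis or decision rule (SAP section 4), and that a group under 10 would already be shown as a listing. Another argument is that the malignancy term was included to catch liver tumours. The SAP does not say so, and a severe tumour does not by itself establish severe hepatic impairment. The definitional gap therefore stands.

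**Conclusion.** The point holds as a defect of definition. Followed as written, SAP section 5.4 can place patients without current hepatic impairment in the only subgroup of this SAP that addresses the severe hepatic impairment item. The malignancy part rests on the plain text and is firm. The past-condition part is an inference from the form content and the absent ongoing rule, and is less certain.

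The real size cannot be obtained from the documents. Under the assumed risks and misclassified shares of 10% to 50%, a reported percentage moves by 2 to 10 points in either direction. The outputs most affected are the survival curve and the adverse event summaries; the death table is partly protected by its breakdown by cause. Because the study is descriptive, this should be corrected before the final outputs, but it does not undermine the study as a whole.

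**What to change.** In SAP section 5.4:

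1. Remove gastrointestinal malignancy as a stand-alone qualifier. Count such patients only if a severe hepatic impairment term is also recorded.
2. Require the qualifying term to be ongoing at the treated-set baseline defined in section 8.2.
3. State that severe applies to every listed term.
4. Report the number of patients by qualifying term beside each output for this subgroup.

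Raw baseline bilirubin and transaminases may be listed where available. They cannot be graded against the upper limit of normal, because the SAP's amendment table states that the database does not hold those limits. Values may also be missing, since assessments are recommended and not required.

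The cost is SAP wording, a programming filter and one count table. The subgroup becomes smaller and may be reported only as a listing, which section 5.4 already provides for. One limit remains: a severe grade on a hepatic diagnosis would still stand in for severity of impairment, so the report should say that the group is defined by recorded terms.

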### **9.2.1. Inclusion Criteria**

Patients must meet all of the following inclusion criteria to be eligible for inclusion into THAOS:

1. Evidence of a personally signed and dated informed consent document indicating that the patient (or a legally acceptable representative) has been informed of all pertinent aspects of the study.
2. Males and females  $\geq 18$  years of age.
3. Confirmed genotyped TTR mutation with or without a diagnosis of hereditary or wild-type ATTR amyloidosis. Confirmation of ATTRwt amyloidosis will be determined by genotyped confirmation that patient does not possess a known mutation in TTR gene (ie, is a carrier of wild-type allele only) via genetic testing and one of the following set of criteria (a, b, or c):
  - a. Presence of amyloid in cardiac biopsy tissue confirmed as TTR amyloid by mass spectrometry or immunohistochemistry; or

- b. Evidence of cardiac involvement by echocardiogram as defined by left ventricle wall thickness of >12 mm, and presence of amyloid in non-cardiac tissue confirmed as TTR amyloid by mass spectrometry or immunohistochemistry; or
- c. No evidence of primary (light chain) amyloidosis, and presence of amyloid in cardiac tissue indirectly confirmed by scintigraphy with a “bone seeking tracer” eg, 99mTC-DPD [99mTC-3,3-diphosphono-1,2-propano-dicarboxylic acid], 99mTC- PYP [Pyrophosphate], and 99mTC-HMDP [hydroxymethylene diphosphonate] with Perugini grade  $\geq 2$ .

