### **Study population**

The THAOS study population includes enrolled patients with confirmed ATTRh or ATTRwt amyloidosis and those with a TTR gene variant without a diagnosis of ATTR amyloidosis.

TTR genotyping is required to confirm eligibility and will be performed before the Eligibility/Baseline visit and outside of the auspices of the survey according to the site's standard practices. For patients with a documented TTR variant, the variant(s) is recorded in the patient's medical record.

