## 2.2 STUDY OBJECTIVES

The objectives of THAOS are to:

- Describe the population of patients affected with ATTR amyloidoses;
- Enhance the understanding of disease natural history, including the variability and progression of the hereditary and acquired forms of the disease;
- Better understand the genotype – phenotype relationship in ATTRv;
- Compare the progression of disease and overall survival in patients with ATTR amyloidosis with and without liver transplant;
- Foster an international community of medical experts who will develop recommendations on the clinical management of ATTR amyloidoses;
- Provide information to better understand the management and treatment of patients with ATTR amyloidoses through publication of the survey data;
- Provide information on off-label use of tafamidis by identifying patients who do not meet the inclusion criteria for transthyretin amyloid cardiomyopathy (ATTR-CM)
- For tafamidis-treated patients, collect and summarize all AE/SAE data, including for the specific safety concerns outlined in Table 1 Summary of Safety Concerns to be Assessed in THAOS comprising important identified risks, important potential risks, and missing information that includes long-term safety in ATTR-CM patients with **CCI** [REDACTED] Class IV.
- For patients not treated with tafamidis, collect and summarize additional data on the events of interest listed in Table 1.

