#### **5.1 ALL ENROLLED**

This analysis set will include patients who have been enrolled in THAOS study and have signed the informed consent form.

The enrollment date will be considered as the date when informed consent form (ICF) was signed.

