## 5.2 TAFAMIDIS UNTREATED

The tafamidis untreated set will include the following:

- All available data from patients who have been enrolled in THAOS, signed the informed consent and who have not received tafamidis during the THAOS study.
- All available data before receiving the first dose of tafamidis while in THAOS, for those patients who were not on tafamidis during or after initial enrollment in THAOS but then started receiving tafamidis post enrollment.

Note: Available data after a patient discontinues treatment with tafamidis will be excluded (See Figure 1)

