### 8.2.6 Safety Analyses

#### Survival Analyses

Mortality will be analysed using the Kaplan Meier method with median survival times (if estimable) and 95% CIs if the number of events are at least 5.

Mortality will be summarized and presented by plots for the following sets: tafamidis treated set by phenotype at enrollment and overall, tafamidis untreated set by phenotype at enrollment and overall, CCI and either predominantly cardiac or mixed phenotype at enrollment, tafamidis treated set for patients who had severe hepatic impairment at baseline, tafamidis

untreated set by their liver transplantation status (liver transplant prior to enrollment/liver transplant after enrollment/no liver transplant), tafamidis treated set by liver transplantation status (liver transplant prior to first dose of tafamidis/liver transplant after the first dose of tafamidis/no liver transplant).

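### The untreated liver-transplant strata carry no diagnosis condition, so undiagnosed mutation carriers enter the no-transplant survival comparator

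*SAP*

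**What the plan says.** SAP 2.2 and Protocol section 8 state the objective. In the SAP's words it is to "Compare the progression of disease and overall survival in patients with ATTR amyloidosis with and without liver transplant".

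Eligibility is wider than that. Protocol 9.2.1, criterion 3, admits "Confirmed genotyped TTR mutation with or without a diagnosis of hereditary or wild-type ATTR amyloidosis", and the SAP study population (section 2.1) likewise includes "those with a TTR gene variant without a diagnosis of ATTR amyloidosis".

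The analysis sets do not narrow it:
- All enrolled (SAP 5.1): "This analysis set will include patients who have been enrolled in THAOS study and have signed the informed consent form".
- Tafamidis untreated (SAP 5.2): patients who were enrolled, "signed the informed consent and who have not received tafamidis during the THAOS study", plus pre-treatment data from those who start tafamidis later.

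SAP 5.4 then defines three liver-transplant strata among patients not on tafamidis at enrollment: transplant before enrollment, transplant after enrollment, and neither. The third is "Patients not on tafamidis at the time of enrollment on THAOS without any liver transplant either before or after enrollment on THAOS".

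The Survival part of SAP 8.2.6 begins "Mortality will be summarized and presented by plots for the following sets" and lists the untreated set by these three transplant categories. The Deaths part does the same. In the SAP 8.2.8 grid the three strata have their own columns, not crossed with phenotype or diagnosis. Survival time in the untreated set runs from enrollment (SAP 6.2.1).

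**The concern.** The objective names people with the disease; the strata that serve it are built from tafamidis status and transplant status alone. Protocol 7.1 lists orthotopic liver transplantation as a disease-modifying therapy for ATTR-PN and combined heart and liver transplantation as an option for ATTR-CM. A carrier without disease has little reason to receive either, so carriers can be expected to collect in the no-transplant stratum and to contribute follow-up there from the day of consent.

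The same stratum takes in ATTRwt patients. They do have ATTR amyloidosis, but Protocol 7.1 describes wild-type disease as mainly affecting elderly men, and nowhere lists liver transplant alone as a therapy for them.

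At stake is whether the survival display for a stated comparative objective can be interpreted. The no-transplant curve would mix disease-free carriers, hereditary disease and wild-type disease in proportions that the display does not show. A reader comparing it with the transplant curves would be comparing different populations as well as different treatment histories.

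**Working it through.** **1. Trace of the population.** The objective requires ATTR amyloidosis. Each later step was checked for a condition that would restore it.

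| Step | Condition applied | Diagnosis required? |
|---|---|---|
| Protocol 9.2.1, mutation carriers | genotype | no |
| Protocol 9.2.1, ATTRwt | amyloid evidence (a, b or c) | yes, in effect |
| SAP 5.1 / 5.2 | enrollment, consent, tafamidis status | no |
| SAP 5.4 transplant strata | tafamidis status at enrollment, transplant status | no |
| SAP 8.2.6 Survival, Deaths; 8.2.8 | the strata as defined | no |

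The Asymptomatic phenotype (SAP 5.4) and recorded diagnosis status (SAP 8.2.3) both exist, but neither is applied to these strata. No readable text supplies a filter.

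**2. Inputs for the size.** The documents give no carrier share, event count or sample size, so there is no plan figure to reproduce. What follows is an illustration.
- Mean survival with disease, m: 10 or 15 years, the Protocol 7.1 range for ATTR-PN, measured there from first symptoms. *Assumed* here to act as a constant hazard from enrollment.
- Carrier death rate, h: 0.002 to 0.01 per year. *Assumed.*
- Carrier share of the stratum, f: 20% and 40%. *Assumed.*

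**3. Pooled 5-year mortality.** (1 − f)(1 − e^(−5/m)) + f(1 − e^(−5h)).

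Components: disease 1 − e^(−0.5) = 39.3% (m = 10) and 1 − e^(−1/3) = 28.3% (m = 15); carriers 1 − e^(−0.01) = 1.0% and 1 − e^(−0.05) = 4.9%.

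| f | m = 10, h = 0.002 | m = 10, h = 0.01 | m = 15, h = 0.002 | m = 15, h = 0.01 |
|---|---|---|---|---|
| 0 | 39.3% | 39.3% | 28.3% | 28.3% |
| 20% | 31.7% | 32.5% | 22.9% | 23.7% |
| 40% | 24.0% | 25.6% | 17.4% | 19.0% |

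Example, f = 40%, m = 15, h = 0.01: 0.6 × 28.35% + 0.4 × 4.88% = 18.96%. Relative to disease mortality the loss is 1 − 18.96/28.35 = 33%. At the other extreme (m = 10, h = 0.002) it is 1 − 24.01/39.35 = 39%.

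**4. The same effect as a rate ratio.** Suppose transplant has no effect, and divide the disease rate 1/m by the stratum's deaths per person-year over 5 years. With 20% carriers, m = 15 and h = 0.01:
- deaths per patient: 0.8 × 0.2835 + 0.2 × 0.0488 = 0.2365
- person-years per patient: 0.8 × 0.2835 × 15 + 0.2 × 0.0488/0.01 = 4.377
- rate 0.0540; ratio 0.0667/0.0540 = 1.23

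The range over the assumed values is 1.23-1.31 at 20% carriers and 1.39-1.53 at 30%.

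**5. What is not modelled.** ATTRwt patients in the stratum are left out, because the documents give neither their share nor their mortality. Steps 3 and 4 therefore show one of two opposing influences, not the net bias.

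**The case against.** The strongest reply is that this is a descriptive registry (SAP section 4), that carriers are a declared part of its population, and that Protocol 9.9 already acknowledges selection bias and confounding. That is true, but a descriptive curve must still describe the population its objective names. Protocol 9.9 looks to matching or regression, whereas SAP 8.1 is descriptive and no adjustment appears in the readable survival section. Restriction is the control left, and it is absent.

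Other objections stand and limit the point:
- A reader might infer that the comparator consists largely of people without the disease. The documents give no carrier count, so only an unknown, possibly large, share can be claimed.
- A reader might infer from the rate ratios that the bias runs against transplant. ATTRwt patients may pull the other way, so the net direction is unknown.
- A reader might extend the criticism to the untreated overall mortality curve. That curve is shown beside by-phenotype results, Asymptomatic is one of the defined phenotypes, and Protocol 9.7.2 prespecifies whole-group reporting. A label is enough.
- A reader might extend it to the treated transplant strata. Commercial tafamidis is given according to the label, which implies disease, so they need no change.
- The progression analyses and one survival subgroup are redacted. The point is therefore confined to Survival and Deaths.

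**Conclusion.** The point holds for the three liver-transplant strata of patients not on tafamidis at enrollment. Followed as written, the SAP places undiagnosed carriers in the no-transplant comparator of an objective about patients with ATTR amyloidosis. This is a mismatch between objective and analysis, not a missing detail. It rests on the readable definitions alone and needs no assumption about numbers.

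The size does need assumptions. The carrier effect alone would lower 5-year mortality from 28-39% to about 23-33% at a 20% carrier share and 17-26% at 40%. That depends on the assumed shares and carrier death rates, and on applying an ATTR-PN mean from first symptoms as a constant hazard from enrollment. These figures show that a moderate share could matter; they do not estimate the bias in THAOS.

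**What to change.** In SAP 5.4, 8.2.6 (Survival and Deaths) and 8.2.8:
- Restrict the three untreated liver-transplant strata to patients with a recorded diagnosis of ATTR amyloidosis at enrollment. Do not use symptomatic status as the filter: SAP 5.4 classes ATTRwt patients as predominantly cardiac whether symptomatic or not, so it would drop diagnosed patients, and the Asymptomatic phenotype is not the same as having no diagnosis.
- Present ATTRv separately from ATTRwt within these strata.
- Report undiagnosed carriers separately.
- Keep the untreated overall curve as prespecified, labelled as including undiagnosed carriers. Leave the treated strata as they are.

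Diagnosis status and genotype are already summarised under SAP 8.2.3, so no new data collection is needed. The cost is SAP wording and a programming filter. Strata become smaller, and some may fall under the existing display rules (listings below 10 patients, no Kaplan-Meier estimates below 5 events). Carriers diagnosed after enrollment, including any transplanted later, leave the comparison; the SAP should say so.
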